### **Summary tables**

- Summary statistics of raw values and change from BL by visit and by on/off trt (serum only)
- Frequency table for participants who had any increase together with the information about recovery (yes/no) at the end of observation.
- Repeat for subgroup of participants with at least 9 weeks of treatment

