- Increased serum neurofilament light chain (sNfL) levels observed in more than half of the participants after 9 weeks on treatment
- Decreased amplitude in the sural nerve (SNAP) compared to baseline in the 3 participants with both an increase in sNfL and decreased or absent DTRs
- Paresthesia in the lower extremities was reported by two participants. One resolved on treatment within 5 days and one led to early treatment discontinuation and subsequently resolved.

In this communication:

Participants that were actively taking study treatment at the time were instructed to stop the study treatment immediately and to return to the site for an on-site visit no later than 7 business days after being informed of the USM. The USM letter provided details on the assessments to be conducted during that visit. Subsequent to this on-site visit participants were to continue to adhere to their monthly visit evaluation schedule for on-site visits as per protocol (e.g., Week 9, 13, 17, 21, 25 etc.) until further notice. During these visits, all scheduled assessments were to be performed as per protocol with the following exceptions:

- Study drug should no longer be taken by participants
- PK [REDACTED] including mHTT/HTT (plasma [REDACTED]) [REDACTED] should only be collected up to 6 weeks after the last dose of study drug. The 0-Hour timepoint (pre-dose in the protocol pre-USM) is the only required timepoint for collection.
- No additional lumbar puncture will be scheduled thereafter unless deemed necessary by the investigator.
- Follow-up Nerve Conduction Study (NCS) evaluation may be required on a case-by-case basis, in consultation with the DMC.

Participants that had already permanently discontinued study treatment and had scheduled an End of Treatment (EOT) and/or follow up assessments at the time of this USM were to continue the previously agreed upon schedule of assessments as per discussions between investigator and Sponsor.

Subsequently a **Follow-up IN (24-Oct-2022)** was sent to sites to provide an update on activities related to the ongoing study following the initial communication on 05-Aug-2022. No new changes were implemented as the purpose was to remind of the above schedule of assessments exceptions.

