As per the USM, participants were to continue with their original VES up to and including Week 29. A new VES was created for Weeks 33, 53 and 69 (see [Table 8-5](#)).

The assessment schedule ([Table 8-2](#), [Table 8-3](#) and [Table 8-4](#)) lists all of the assessments and when they are performed. All data obtained from these assessments must be supported in the participant's source documentation, as appropriate.

Participants should be seen for all visits/assessments as outlined in the assessment schedule or as close to the designated day/time as possible. Refer to [Table 8-1](#) for allowable visit windows. Missed or rescheduled visits should not lead to automatic discontinuation.

If the end of the Blinded Extension has not been triggered by the time participants reach week 53 (i.e., because the results of the DRF are not available), the BE will continue beyond week 53. Participants beyond Week 53 will remain on the assigned dose until the End of Blinded Extension is triggered. Refer to [Table 8-3](#).

The Baseline visit in the OLE is equivalent to the End of Treatment (EOT)-Blinded Extension visit for participants who are still ongoing at the time the End of the BE is declared. Investigators will be notified ahead of time in preparation for transition to OLE. Since the duration of the BE may be different for individual participants, and in order to minimize participant burden, guidance will be provided to Investigators to clarify what BE assessments may be deferred at the final regular BE visit to ensure that they are performed only once as part of the OLE baseline visit, such as LP and MRI.

If the COVID-19 or similar pandemic limits or prevents on-site study visits, alternative methods of providing continuing care may be implemented. Phone calls, virtual contacts (e.g. teleconsult) or visits by site staff/home nursing service to the participant's home depending on local regulations and capabilities, may replace on-site study visits, for the duration of the pandemic until it is safe for the participant to visit the site again. If the Investigator delegates tasks to an off-site healthcare professional, the Investigator must ensure the individual(s) is/are qualified and appropriately trained to perform assigned duties. The Investigator must oversee their conduct and remain responsible for the evaluation of the data collected.

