Days	1	29	57	85	113	141	169	197	225	253	281	309	337	365	999
Weeks	1	5	9	13	17	21	25	29	33	37	41	45	49	53	143

that they are performed only once as part of the OLE baseline visit, such as LP and MRI.

² Participants who discontinue study treatment should be scheduled for an EOT Open-label visit at which time all of the assessments listed for the EOT open-label visit will be performed. A 30-day safety follow up period after the last open label study treatment dose was taken must be observed.

³ Findings must be recorded on the appropriate Adverse Events eCRF

⁴ Male patients only

⁵ Serum pregnancy test is collected as part of the blood chemistry. Refer to [Section 8.4.3](#) for positive result follow up action

⁶ Urine dipstick done at site; if findings then send urine to central lab for microanalysis

⁷ Echocardiogram with GLS

⁸ For visits where samples are collected only once a day, they must always be collected at approximately the same time of the day

⁹ Serum Biomarkers, including NFL. See Biomarkers Assessments in Blood and CSF, [Section 8.5.3](#)

¹⁰ Pre-dose

¹¹ Randomization will be done if there is more than one dose chosen

¹² IRT call and drug preparation by site personnel

¹³ Weekly dosing, not reflected on the VES, should be confirmed with weekly telephone calls to the participant and will be collected on the eCRF.

¹⁴ Update as necessary

¹⁵ To minimize burden to patients, it is recommended that Post-baseline MRI and UHDRS assessments are done up to 1 day prior to the planned study drug dosing date at any given visit. If done same day as Lumbar Puncture, MRI and UHDRS should be done first

The table below (see [Table 8-5](#)) reflects the changes in the USM follow-up notification dated 06-Dec-2022.

Participants randomized to placebo do not require additional safety assessments and can be discontinued from the study at the Week 33 visit or immediately if this visit was already completed. The End of Treatment and End of Study (EOS) dispositions can be declared. Participants that had already permanently discontinued study treatment and had scheduled an EOT and/or follow up assessments at the time of the USM follow-up notification dated 06-Dec-2022 should have follow up (FU) assessments as closely as possible to Assessment [Table 8-5](#).

Table 8-5 Assessment Schedule Urgent Safety Measure

Period	Revised follow-up assessment schedule ³			
Visit Name	Wk 33	Wk 53	Week 69	EOS
Days	225	365	477	477
Weeks	33	53	69	69
Physical Examination	S	S	S	

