## 2.11 Biomarkers

### 2.11.1 NFL in serum and CSF

Serum and CSF NFL levels are used to monitor neurotoxicity.

Visit level Flags:

- on/off treatment (serum only)
- sNFL > 100 pg/mL
- sNFL > 2 x BL sNFL
- sNFL: > 100 pg/mL or > 2 x BL
- sNFL recovery: for participants who met the criterion for any increase of sNFL (sNFL > 100 pg/mL or sNFL > 2 x BL sNFL) at any visit: Flag the visits after last visit with increase that criteria are no longer met (sNFL ≤ 100 pg/mL and sNFL ≤ 2 x BL sNFL)
- CSF NfL > 10000 pg/ml
- CSF NfL > 2 x BL CSF NfL
- CSF NfL > 2 x CSF NfL of the previous assessment
- CSF NfL > 2 x BL CSF NfL or CSF NfL > 2 x CSF NfL of the previous assessment
- CSF NfL > 10000 pg/ml or CSF NfL > 2 x BL CSF NfL or CSF NfL > 2 x CSF NfL of the previous assessment
- CSF NfL recovery: for participants who met the criterion for any increase of CSF NfL at any visit: Flag the visits after last visit with increase that criteria are no longer met (CSF NfL ≤ 10000 pg/ml and CSF NfL ≤ 2 x BL CSF NfL and CSF NfL ≤ 2 x CSF NfL of the previous assessment)

Participant level flag:

- Participant without any increase in sNFL
- participants with any increase in sNFL
- participants with any increase in sNFL followed by recovery (sNFL ≤ 100 pg/mL and sNFL ≤ 2 x BL sNFL)
- Participant without any increase in CSF NfL;
- participants with any increase in CSF NfL;
- participants with any increase in CSF NfL followed by recovery (CSF NfL ≤ 10000 pg/ml and CSF NfL ≤ 2 x BL CSF NfL and CSF NfL ≤ 2 x CSF NfL of the previous assessment)

Note that, flags will be created based on weekly basis window instead of protocol scheduled visit window.

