### **Figures**

- sNFL: spaghetti plot of raw values (log scale for sNFL) over time (in weeks) and by treatment group using color coding to show on/off treatment (line changing color) and add dot color to represent criteria
- CSF: spaghetti plot of raw values over time (in weeks) and by treatment group with colored dots highlighting values meeting criteria

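### The NfL recovery table (SAP 2.11.1) counts participants never re-tested after their first increase as not recovered, which matters mainly for CSF NfL

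*SAP*

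**What the plan says.** **SAP 2.11.1, flags.** For CSF the visit-level rule is "for participants who met the criterion for any increase of CSF NfL at any visit: Flag the visits after last visit with increase", provided the thresholds are no longer met. The serum rule has the same form. At participant level each fluid has three states: no increase, any increase, and an increase followed by recovery. None requires a later sample. The on/off-treatment marker is restricted to serum ("on/off treatment (serum only").

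**SAP 2.11.1, outputs.** The table is a "Frequency table for participants who had any increase together with the information about recovery (yes/no) at the end of observation", repeated for participants with at least 9 weeks of treatment. The figures include "CSF: spaghetti plot of raw values over time (in weeks) and by treatment group with colored dots highlighting values meeting criteria".

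**Protocol, CSF sampling.** Table 16-7 plans post-dose CSF biomarker samples in the first year at Days 57, 113, 225 and 365. The Amendment 02 rationale, describing the USM of 05-Aug-2022, says: "No additional lumbar puncture will be scheduled thereafter unless deemed necessary by the investigator". Section 8 says that "participants were to continue with their original VES up to and including Week 29", but the puncture exception applies within that schedule. Table 8-5 ("Assessment Schedule Urgent Safety Measure"), covering Weeks 33, 53 and 69, lists serum NfL at each visit and has no lumbar puncture row.

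**The concern.** Section 2.11.1 uses NfL to monitor neurotoxicity. The protocol reports raised NfL in serum and/or CSF in most of the active arm. With dosing stopped, whether the increases resolve is one of the main questions left, and this table is where a reader will look.

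A recovery percentage needs a denominator of people in whom recovery could have been seen. As specified, the denominator is everyone with an increase, and those without a later sample are counted as failures. A reader cannot tell *still raised* from *not re-tested*, and a low CSF figure could reflect the end of lumbar punctures as much as persistent injury.

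**Working it through.** The documents give no counts of increases, re-tests or recoveries, so there is no figure to reproduce. The check applies the flags to possible sample sequences, then to the puncture schedule.

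**1. What *no* means.** R is a raised post-baseline sample, N one that is not raised.

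| Sequence | Sample after first rise? | Table entry |
|---|---|---|
| R, N | yes | yes |
| R, R | yes | no |
| R, N, R | yes | no |
| R only | none | no |
| N, R | none | no |

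*No* means only that the last available sample was raised. The last two rows were never re-tested after the first rise, yet they sit with rows two and three. A Week 9 rise that has cleared by Week 17 does count as recovery.

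**2. When a planned CSF re-test existed.** As one possible reading, suppose planned punctures ended on 05-Aug-2022. Then:

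latest first dose = 05-Aug-2022 − (puncture day − 1)

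- Day 57: minus 56 days = 10-Jun-2022
- Day 113: minus 112 days = 15-Apr-2022
- Day 225: minus 224 days = 24-Dec-2021

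The visit windows in Protocol Table 8-1 move the first two dates by one day and the third by up to a week. The SAP Document History dates the first version 30-Nov-2021, before FPFV (taken as first patient, first visit). Screening runs from Day −42 to Day −7, so the earliest first dose is about 30-Nov-2021 + 7 days = 07-Dec-2021. On this reading, a first rise at Week 17 could be re-tested by a planned puncture only for first doses between about 07 and 24-Dec-2021. A first rise at Week 9 had no planned re-test for anyone first dosed after 15-Apr-2022.

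The repeat in participants with at least 9 weeks of treatment does not cure this, because the second planned puncture is at Day 113.

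**3. Size.** Let u be the share of those with an increase who have no later sample, and r the recovery proportion among those re-tested.

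- Table shows: (1 − u) × r
- Upper limit for everyone with an increase: (1 − u) × r + u

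Both inputs are assumed. Each cell gives the shown figure, then the upper limit.

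| | u = 10% | u = 25% | u = 50% |
|---|---|---|---|
| r = 40% | 36%, 46% | 30%, 55% | 20%, 70% |
| r = 60% | 54%, 64% | 45%, 70% | 30%, 80% |
| r = 80% | 72%, 82% | 60%, 85% | 40%, 90% |

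In counts (also assumed): 12 with an increase, 6 never re-tested and 3 recovered gives 3/12 = 25% in the table and 3/6 = 50% of those re-tested.

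**4. Serum.** Serum NfL stays on the original schedule to Week 29, then is taken at Weeks 33, 53 and 69 in the active arm. Non-assessment is limited to dropouts, missed visits and a first rise at the last visit.

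**5. A separate minor point, not about NfL.** In SAP 2.7.4.4 (neurological exam) and 2.7.4.5 (questionnaire), full recovery means all worsened parameters or items resolved and partial recovery means one or more. With k worsened items, full is {k} and partial is {1, …, k}, so every full recoverer is also a partial recoverer, and for k = 1 the two are identical. The table in 2.7.4.6 (nerve conduction) reports a partial recovery that the section's flags do not define.

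**The case against.** The best defence is that the table reports status at last observation in a descriptive, abbreviated study report, with about 20 active participants planned in Cohort 1 (about 25 at 4:1). The CSF plot shows each trajectory with raised values marked, so single-sample participants can be seen. This stands as mitigation: a careful reader could recover the split from the figure. It does not correct the percentage in the table.

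A reader might go further and use the dates above to list exactly which participants could never be shown to recover. The documents do not support that:

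- The ban on further punctures may run from the USM itself or from the on-site visit due within 7 business days of being informed. That visit's assessments were set in a letter that is not reproduced, so it may or may not have included a puncture.
- The neighbouring limit, "should only be collected up to 6 weeks after the last dose of study drug", covers PK and blood biomarkers. Nothing extends it to punctures. It also runs from each participant's own last dose, so 08-Aug-2022 + 42 days = 19-Sep-2022 is only a latest possible date.
- Investigators could request punctures, and participants who stopped early kept previously agreed schedules.

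It is also tempting to say that CSF alone lacks an on/off-treatment split. The serum recovery table is not split either, since the marker applies to the summary statistics and the plot. If planned punctures ended at the USM, nearly all planned CSF samples in those still dosing were on treatment. The split would help mainly for early stoppers and requested punctures.

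**Conclusion.** The point holds as a reporting defect. The *no* category pools not re-tested with re-tested and still or again raised, and the *yes* percentage can understate recovery among those re-assessed. This follows from the flags as written and does not depend on any reading of the USM. That it bites mainly on CSF rests on the end of routine punctures and the absence of any in Table 8-5. A first rise at Week 17, or at Week 9 in later-dosed participants, would often have had no planned re-test.

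The number affected is unknown, and the percentages above are illustrations over an assumed range. The change is worth making, but its effect is modest.

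Two stronger inferences fail. Partial recovery is no part of the NfL table, so its loose definition does not affect NfL. Nor is the partial row in 2.7.4.4 shown to be overstated: that table lists consecutive worsening beside partial and full recovery, and both recovery groups are subsets of it, so its categories are already nested.

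**What to change.** In the NfL recovery table, for serum and CSF separately, report three exclusive outcomes anchored to the first increase:

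1. recovered at last assessment;
2. re-assessed after the first increase and still or again raised at last assessment;
3. no assessment after the first increase.

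Give the recovery percentage among all with an increase and among those re-assessed (1 + 2), each with its n. For CSF, also give the time from last dose to last sample, or on/off-treatment status using the existing definition in SAP 2.1.1 (on treatment up to last dose + 13 days). Add the same no-later-assessment category to the table in SAP 2.7.4.7, which has the same yes/no form for nerve conduction, exam and symptom findings.

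Separately, in SAP 2.7.4.4 to 2.7.4.6, define partial recovery as at least one but not all of the worsened parameters, items or (for nerve conduction) sides resolved.

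The cost is SAP wording and minor programming, with no new data. The downside is smaller denominators among those re-assessed.

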### **Figures**

- sNFL: spaghetti plot of raw values (log scale for sNFL) over time (in weeks) and by treatment group using color coding to show on/off treatment (line changing color) and add dot color to represent criteria
- CSF: spaghetti plot of raw values over time (in weeks) and by treatment group with colored dots highlighting values meeting criteria

### **2.11.2 mHTT in CSF**

#### **Summary tables**

- Summary statistics of raw, change, % change and annualized % change by visit
- Difference between active and placebo for % change by visit
- Mean time (in days) from last dose to LP for week 9 and 17 (protocol scheduled visit window will be used to derive week 9 and week 17)

Days from last dose to LP = date of {LP} - date of {previous dosing date}

Note, if a dose is taken on the same day of LP performed, the previous dosing date should be used instead of the same day dosing.

### **Figures**

- Spaghetti plot of % change over time (at actual weeks) and by treatment group
- Average % change from baseline with error bars will be provided by group (at scheduled timepoint, summary statistics and N will be added on x-axis)

## 2.13 Interim analysis (IA)

IA was performed in April 2023 to share information about the Phase IIb study with broader HD community at HDTc (Huntington's Disease Therapeutics Conference). Analysis plan for IA can be found in SubWay.

### 3 Sample size calculation

Sample size is determined by feasibility and is evaluated using the primary endpoint mHTT reduction in CSF from baseline to Week 17.

### 3.1 Primary endpoint(s)

In the analysis, all participants assigned to matching placebo in different treatment arms will be pooled together as one placebo group.

The Multiple Comparison Procedure – Modelling (MCP-Mod) methodology ([Bretz et al 2005](#) and [Pinheiro et al 2014](#)) will be employed to test for an overall dose response (DR) signal and to estimate the DR curve. Five candidate sigmoidal Emax models will be used for the testing step with parameter (ED50, h) being (5, 1), (20, 2), (50, 1), (50, 3), and (90, 6).

For the primary endpoint of mHTT reduction in CSF, the planned minimum sample size of N = 75 for 3 dose arms (3 active treatment groups with n = 20 each and a placebo group with n = 15) will be sufficient to reach > 80% power on average for detecting DR signal using MCP-Mod methodology (under the MCP step) with one-sided significance level of 5%. Power will be higher if Cohort 3 and/or Cohort 4 are initiated (N=80 and 100 respectively). The calculations are based on assumption of 40% mHTT lowering in CSF (for the highest dose) and 0% mHTT lowering for placebo. The assumptions on SD were based on [Tabrizi et al 2019](#). An inflation factor of 50% has been applied to the SD of both the active groups (SD = 0.195) and placebo group (SD = 0.471) in order to be conservative leading to an overall treatment effect size of 1. The sample size calculation is performed in RStudio 3.6.1 using package "DoseFinding".

For the safety endpoint, no formal sample size calculation is performed. In general, AEs/SAEs with higher incidence rate will be identified more likely. Low incidence AEs/SAEs are less likely to be observed until later in the study when there are more participants recruited. [Table 3-1](#) presents the likelihood to identify AEs/SAEs at different timing of the cohort gating assessments and interim analysis.

**Table 3-1 Likelihood of Identifying AEs/SAEs with Hypothetical Incidence Rate**

Time of Assessment	# in active group	Incidence rate	Likelihood to observe at least one AE/SAE
Cohort Gating Assessment 1	16	1%	15%
	5%	56%	
	10%	81%	
Cohort Gating Assessment 2	24	1%	21%
	5%	71%	
	10%	92%	
Cohort Gating Assessment 3	32	1%	28%
	5%	81%	
	10%	97%	
Interim analysis	Minimum 60	1%	45%
	5%	95%	
	10%	99%	

### 3.2 Secondary endpoint(s)

The study is not powered for secondary endpoint.

## 4 Change to protocol specified analyses

See above.

## 5 Appendix

### 5.1 Imputation rules

If the visit date(s) is missing, no imputation will be implemented.

#### 5.1.1 Study drug

Start date and end date of study drug on the respective CRF panel are mandatory; thus, no date imputation will be applied.

#### 5.1.2 AE date imputation

To decide whether the event was prior or post-dosing is carried out as follows:

- If start date and time are not missing, then report as post-dosing if start date and time > dosing start date and time
- If start date is available, but not start time, then report as post-dosing if start date > dosing start date. This means that all events occurring on the dosing start day (even if they occurred prior to it) will be considered as post-dosing.
- If both start date and time are missing, the event will be defined as being post-dosing.

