### 2.7.1 Adverse events (AEs)

AEs will be considered as treatment-emergent (TEAE) if the event is starting after the start of double-blind treatment or the event is present prior to start of double-blind treatment but increased in severity after the start of treatment based on preferred term. This assumes the same AE with increased severity is properly entered as a separate record in the database with start date being the date when severity increases and that a second AE with same severity won't be entered before the same AE is resolved.

Adverse events will be coded using the MedDRA dictionary and presented by system organ class (SOC) and preferred term (PT). The MedDRA version used for reporting the study will be described in a footnote on AE related outputs.

Additionally, Participant with AEs indicative of neurotoxicity / peripheral neuropathy (listed in [Table 2-3](#)) will be flagged at participants level for recovery.

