### Summary tables

The number (and percentage) of participants with TEAE will be summarized by treatment group and presented by the SOCs in alphabetical order and the PTs in descending incidence in the total column. A patient with multiple AEs within a given category is only counted once for summary purposes. TEAEs, regardless of study drug relationship, will be summarized in the following ways:

- By treatment and PT
- By treatment and SOC
- By treatment, SOC and PT
- By treatment, SOC, PT and maximum severity

Separate summaries by SOC and PT will be provided for:

- TEAEs suspected to be study medication related
- TEAEs leading to treatment discontinuation
- TEAEs leading to dose interruptions and/or adjustments
- Serious treatment emergent AEs

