### Listings

Listing will be provided for all AEs and SAEs.

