**Table 5-1 Imputation of start dates**

Missing elements	Rule
Day, month, and year	
The date uncertainty is too high to impute a rational date. Therefore, if the year value is missing, the imputed start date is set to NULL.

Day and month	

• If available year = year of study treatment start date then

– If end date contains a full date and end date is earlier than study treatment start date then set start date = 01JanYYYY

– Else set start date = study treatment start date.

• If available year > year of study treatment start date then 01JanYYYY

• If available year < year of study treatment start date then 01JulYYYY

Day	

• If available month and year = month and year of study treatment start date then

– If end date contains a full date and end date is earlier than study treatment start date then set start date= 01MONYYYY.

– Else set start date = study treatment start date.

• If available month and year > month and year of study treatment start date then 01MONYYYY

	

• If available month and year < month year of study treatment start date then 15MONYYYY

--	--

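### SAP 5.1.2: the date-only rule for adverse events uses a strict inequality that contradicts its own explanation for untimed events on the first dosing day

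*SAP*

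**What the plan says.** SAP 5.1.2 has three bullets for classing an adverse event as prior to or after dosing.

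- **Date and time both known:** the two date-times are compared with a strict inequality.
- **Date known, time missing:** "If start date is available, but not start time, then report as post-dosing if start date > dosing start date". The next sentence of this bullet says: "This means that all events occurring on the dosing start day (even if they occurred prior to it) will be considered as post-dosing".
- **Date and time both missing:** "If both start date and time are missing, the event will be defined as being post-dosing".

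The definition of a treatment-emergent event is in SAP 2.7.1: "AEs will be considered as treatment-emergent (TEAE) if the event is starting after the start of double-blind treatment". It also admits an event that was present earlier but became more severe after treatment began. It does not mention 5.1.2 and has no rule of its own for untimed events on Day 1.

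Two outputs in 2.7.1 matter here. For the tables, "The number (and percentage) of participants with TEAE will be summarized by treatment group". For the listings, "Listing will be provided for all AEs and SAEs". SAP 5.1.3 applies the adverse event date rule to concomitant medication as well.

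**The concern.** The second sentence of the date-only bullet is worded as a consequence of the first, but it does not follow from it. A strict greater-than excludes the dosing start day, and the explanation includes it. Two programmers who each follow one half of the bullet would produce different treatment-emergent flags from the same record.

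What is at stake is the count of treatment-emergent events. Safety and tolerability was one of the two original primary objectives and is still reported, now descriptively (SAP 1.2, Table 1-1 and 2.5). With no inferential analysis planned, these counts are themselves the reported result. If the operator is followed, the error goes towards leaving events out.

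**Working it through.** The plan gives no figure to reproduce and no arithmetic is needed. Let D be the first dosing date. Take an adverse event with a known start date and no start time, and compare the operator as printed with the inclusive operator that the explanatory sentence describes.

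| Start date | Strict, as printed | Inclusive, as explained |
|---|---|---|
| before D | prior | prior |
| equal to D | prior (`D > D` is false) | post-dosing (`D >= D` is true) |
| after D | post-dosing | post-dosing |

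The classes differ in the middle row only.

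**The first bullet is not affected.** When a time is recorded, it settles the order on Day 1, so a strict comparison of date-times raises no conflict. The explanatory sentence belongs to the second bullet and is read here as confined to untimed events.

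**Which half is intended.** The explanation says outright that Day 1 events count, even those that may have preceded the dose. The third bullet has the same inclusive default, since an event with no date at all is post-dosing. Under the strict operator, an undated event would count as post-dosing while an event known to fall on the dosing day would not. Having more information would remove the event, which is incoherent. Both points favour the inclusive reading.

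**Whether other text settles it.** The definition in 2.7.1 speaks of events starting after treatment start, but an untimed Day 1 event cannot be ordered against the dose. The Baseline definition in SAP 2.1.1 treats randomization-day assessments as pre-dose where the protocol plans them so; that concerns scheduled assessments, not adverse events. So 5.1.2 is the only rule for this case.

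**Effect on outputs.** If the strict operator sets the flag, an untimed Day 1 event drops out of the 2.7.1 tables unless it later worsens, which 2.7.1 expects to be entered as a separate record. The listings are unaffected. A participant is counted once per category, so one with another qualifying event in the same category would still be counted there.

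**Concomitant medication.** SAP 2.1.1 defines concomitant use from the day of first dose onwards, which already includes Day 1. The operator matters there only if the programs reuse it.

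**The case against.** The strongest reply is that the bullet resolves itself. Its second sentence addresses the disputed case and states the outcome, and no rival rule exists. A programmer would have to ignore the adjacent sentence to go wrong, so this is a one-character slip and not a doubtful choice of analysis. That stands as a description of the fault and is the main reason for rating it minor. It does not make the operator correct. Clear intent makes the correction safe.

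A second reply is that a greater-than-or-equal sign may have been lost when the PDF was read. This cannot be fully excluded: the ejection fraction limit in SAP Table 5-14 is printed as below minus 50%, which may be a damaged symbol. However, the sign survives elsewhere in the SAP, for example in the on/off treatment definition (2.1.1), the nerve conduction flags (2.7.4.6) and Table 5-9. If the source file shows the inclusive sign, the point closes.

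A third reply is that the path from 5.1.2 to the tables is inferred, since 2.7.1 does not cite it. That is fair. The path is the natural reading, because no other rule orders adverse events against dosing, but it is an assumption.

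Last, the consequence is small. Reporting is descriptive, the rule is the same in both groups, and every event is listed. The two neurological findings that the Amendment 02 rationale first reports with a time on treatment, reflex changes after 13 weeks and raised serum neurofilament after 9 weeks, lie far from Day 1. All of this stands.

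**Conclusion.** The contradiction is real and narrow. The date-only operator in SAP 5.1.2 is wrong as written for an untimed event dated on the first dosing day, and for nothing else. The effect on the tables assumes that 5.1.2 sets the treatment-emergent flag and that the operator is coded literally. The number of affected events cannot be derived: the documents give no count of Day 1 events, and protocol 10.1.1 asks for start and end dates without saying whether a time is recorded. It may be zero. Severity: minor.

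A reader might infer two stronger things that the documents do not support.

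- **That partial dates are misclassified too.** In two places Table 5-1 says "Else set start date = study treatment start date", which puts an imputed date exactly on the boundary. But the SAP does not say that imputed dates go back through the 5.1.2 test. The table also diverts an event first under the condition "If end date contains a full date and end date is earlier than study treatment start date", which suggests that the remaining events are meant to count as post-dosing.
- **That a material number of drug-related Day 1 events would be lost.** Protocol 4.5 reports Day 1 diarrhea in 7 of 8 subjects of one healthy-volunteer cohort, but 5 of these received branaplam and 2 placebo. The setting was a different population and dosing regimen. The figure shows neither a drug effect nor the frequency to expect at 56 mg weekly.

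**What to change.** In the second bullet of SAP 5.1.2, replace the strict inequality with `>=`, so that an event with a date but no time is post-dosing when its start date is on or after the dosing start date. Keep the explanatory sentence, which will then follow from the rule. Because SAP 5.1.3 adopts the same rule for concomitant medication, make the same correction there if the operator is reused.

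The cost is one operator in the SAP and the matching line of the program specification. No new data, output or analysis is needed. Citing 5.1.2 from the definition in 2.7.1 would help the reader, but that is editorial and the correction does not depend on it.
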